6. SAMPLE SIZE DETERMINATION

The sample size consists of 80 subjects who have been diagnosed with Chronic Post-COVID-19 - Syndrome.

7. SUPPORTING DOCUMENTATION

7.1. Appendix 1 Study Population Analyses

Unless otherwise specified, the study population analyses will be based on the "Safety" population. Screen failures will be summarized or listed based on the "Screened" population. A summary of the number of participants in each of the participant level analysis set will be provided.

7.1.1. Subject Disposition

A summary of the number and percentage of subjects who completed the study as well as those who withdrawn from the study will be provided by treatment. Reason of study withdrawn will be summarized by treatment.

A summary of the study intervention status will be provided. This display will show the number and percentage of subjects who have completed the Week 26, as well as primary reasons for withdrawn.

The study analysis set will be summarised in the subject disposition table.

The details of the planned displays are in programming specification document.

7.1.2. Demographic and Baseline Characteristics

The demographic characteristics including, age, sex, ethnicity, race, height at baseline, weight at baseline, BMI at baseline will be summarized with descriptive statistics. In addition, the following categories will be summarized: 18-64, 65-84 and >=85 based on the randomised analysis set.

Listings of demographic characteristics will also be produced.

The details of the planned displays are in programming specification document.

7.1.3. Study Intervention Exposure and Compliance

A summary of Overall cumulative exposure to HB-adMSCs will be produced.

The details of the planned displays are in programming specification document.

7.2. Appendix 2 Data Derivation Rule

7.2.1. Criteria for Potential Clinical Importance

The potential clinical importance criteria are not defined this trial. A laboratory value that is outside the reference range is considered either high abnormal or low abnormal will be displayed based on lab normal range data.

7.2.2. Study Period

Adverse events will be classified according to the time of occurrence relative to the study intervention period.

Treatment emergent	Definition
Y	If event start date is not missing and is before date of first dose of study medication.
N	Any event started on or after date of first dose of study medication or event date is missing or partial

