Duration of administration	1 hour
Laboratory Samples.	Screening, Week 0, 6, and 26.

	Screening
Visits by Weeks	Week 0 _ Infusion 1
	Week 2 _ Infusion 2
	Week 6 _ Infusion 3
	Week 10 _ Infusion 4
	Week 14 _ Follow Up 1
	Week 20 _ Follow Up 2
	Week 26 – End of Study

“A randomized, double-blinded, single-center, phase 2 efficacy, and safety study of allogeneic HB-adMSCs for the treatment of patients with Chronic Post-COVID-19 Syndrome.”

Objectives

Primary Objectives

- To investigate the efficacy of intravenous infusions of HB-adMSCs (allogeneic) vs. Placebo in patients with Chronic Post-COVID-19 Syndrome as determined by improvements in individual symptom scores of Visual Analog Scale of Neurological Symptoms. (Time frame: Baseline to Week 26).
- To assess the safety of intravenous infusions of HB-adMSCs (allogeneic) vs. Placebo in patients with Chronic Post-COVID-19 Syndrome as determined by the incidence of adverse events or serious adverse events (Time frame: Baseline to Week 26).

Secondary Objectives

- To investigate the efficacy of intravenous infusions of HB-adMSCs (allogeneic) vs. Placebo in patients with Chronic Post-COVID-19 Syndrome as determined by improvements in individual symptom scores of Visual Analog Scale of Non-Neurological Symptoms. (Time frame: Baseline to Week 26).
- To evaluate the efficacy of intravenous infusions of HB-adMSCs (allogeneic) vs. Placebo in patients with Chronic Post-COVID-19 Syndrome as determined by changes in Fatigue Scale (Time frame: Baseline to Week 26).
- To assess the efficacy of intravenous infusions of HB-adMSCs (allogeneic) vs. Placebo in patients with Chronic Post-COVID-19 Syndrome as determined by changes in SF-36 Quality of life self-assessment. (Time frame: Baseline to Week 26).
- To identify the safety of intravenous infusions of HB-adMSCs vs. Placebo in patients with Chronic Post-COVID-19 Syndrome as determined by changes in Patient Health Questionnaire (PHQ-9).

Endpoints

Primary Endpoints

The efficacy and safety primary endpoints of this study will be evaluated by assessing changes from Baseline to Weeks 26 in the following:

- Visual Analog Scale of Neurological Symptoms. VAS are psychometric measuring tools intended to document the characteristics of disease-related symptom severity in individuals. The neurological symptoms included in this scale are (1) extreme fatigue (2) brain fog, (3) headache (4) sleep disturbances (5) loss of taste/smell.

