- Incidence of treatment-emergent Adverse Events (TEAEs) and serious Adverse Events (SAEs).
- Incidence of AEs of special interest (serious or nonserious), including thromboembolic events, infections, and hypersensitivities.
- Changes in laboratory values, vital signs, weight, physical exam results, and medications used to treat Chronic Post-COVID-19 Syndrome.

Secondary Endpoints

The efficacy and safety secondary endpoints of this study will be evaluated by assessing changes from Baseline to Weeks 26 in the following:

- Subject's energy and stamina as evidenced on the Fatigue Assessment form.
- Visual Analog Scale of non -Neurological Symptoms. The symptoms included in this scale are (1) dyspnea at rest and with activity, (2) cough, (3) body aches, and (4) joint pain.
- Subject's quality of life as evidenced by the Short Form 36 Health Survey Questionnaire.
- Subject's level of depression as evidenced by the PHQ 9 scale.

Investigational Plan.

[figure not shown]
This study is a randomized, double-blind, single-center, phase 2 clinical trial to assess the efficacy and safety of multiple HB-adMSCs (allogeneic) vs. Placebo for treating Chronic PostCOVID-19 Syndrome. The trial includes a screening period of up to 4 weeks, a 10-week treatment period, and a safety Follow-up period of 16 weeks after the last investigational product administration.

This clinical trial will be opened to enroll 80 eligible participants diagnosed with Chronic PostCOVID-19 Syndrome. The study team will conduct patient recruitment. If eligible participants are identified based on eligibility criteria, a screening visit will be scheduled. An informed consent form will be given to the study participants and signed before any study procedures. The informed consent form will include information about the clinical trial, and some aspects should be considered during this process.

- The principal investigator or study team will make sure the participant was alert and able to read and understand the language in the consent form.
- The principal investigator or study team will ensure the participant took ample time to read the consent form carefully.
- The principal investigator or study team will make sure the consent form was carefully explained to the participant, and any questions or concerns were addressed before signing the document.

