10. Twenty-four hours after administration of the investigational product, study participants will be contacted by text or telephone call to assess the incidence of adverse events.

Visit 4 and 5 – Infusion 3 and 4

1. Update medical history and concomitant medications if any change occurred since the last visit.
2. Measure vital signs, including respiratory rate (breaths per minute), body temperature (F), blood pressure (mm Hg), pulse rate (beats per minute), oxygen saturation (%), and weight measurement (lb. or kg).
3. The following baseline vital signs must be met for the infusion to proceed:
 - Pulse rate: ≥ 50 bpm and ≤ 100 bpm
 - SBP: ≤ 160 mmHg and ≥ 95 mmHg**
 - DBP: ≤ 95 mmHg and ≥ 50 mmHg
 - Respiratory rate: ≥ 10 bpm and ≤ 20 bpm
 - Pulse oximeter: $\geq 94\%$ O₂ saturation
4. Physical examination by Principal Investigator.
5. Completion of patient questionnaire including Visual Analog Scale of Symptoms, Fatigue scale and PHQ-9. In addition, during Infusion 4 - SF 36 is required.
6. At infusion the collection of laboratory samples is required - Comprehensive Metabolic Panel (CMP), Complete Blood Count (CBC), Coagulation Panel, and Urine pregnancy test if female of childbearing potential. Urine pregnancy test is required during both visits for female of childbearing potential.
7. Prior to receiving the investigational Product, the study subject should take the following pre-infusion medications: Aspirin 81 mg by mouth, and either Loratadine 10 mg or Cetirizine 10 mg by mouth as needed.
8. Investigational product administration by delegated study personnel. HB-adMSCs or Placebo should only be administered intravenously, with a dosing rate of 4-5ml/min and a vital sign monitoring of two hours (Minutes 0, 15, 30, 45, 60, 90 and 120). The monitoring of vital signs shall be the same as represented in Figure 8.
9. Assess the incidence of any adverse event.
10. Twenty-four hours after administration of the investigational product, study participants will be contacted by text or telephone call to assess the incidence of adverse events.

Visit 6 and 7 – Safety Follow Up Phone Call

1. Update medical history and concomitant medications if any change occurred since the last visit.
2. Assess the incidence of any adverse event since the last visit.

Visit 8 – End of Study

1. Update medical history and concomitant medications if any change occurred since the last visit.

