Sampling tubes, material for shipments of the samples, and a laboratory manual detailing all sample collection and shipment procedures will be provided and distributed to the clinical trial site by the selected laboratory. Laboratory samples will be collected as per protocol during Visit 1 – Screening or Visit 2 – Infusion 1 (Baseline), Visit 5 – Infusion 4, and Visit 8 - End of Study.

Adverse Events

Unanticipated Problems Involving Risk to Subjects or Others

Any incident, experience, or outcome that meets all the following criteria:

- Unexpected in nature, severity, or frequency (i.e., not described in study-related documents such as the IRB-approved protocol or consent form, the investigator's brochure, etc.)
- Related or possibly related to participation in the research (i.e., perhaps related means there is a reasonable possibility that the incident experience or outcome may have been caused by the procedures involved in the study.
- Serious (as defined below) ***“Serious” is different than “severe” as reported in the CTC criteria that apply a grade to the AE.***

Adverse Event

An **adverse event** (AE) is any symptom, sign, illness, or experience that develops or worsens in severity during the study. Intercurrent illnesses or injuries should be regarded as adverse events.

Abnormal results of diagnostic procedures are adverse events if the abnormality:

- results in study withdrawal
- is associated with a serious adverse event
- is associated with clinical signs or symptoms
- leads to additional treatment or to further diagnostic tests
- is considered by the investigator to be of clinical significance

Serious Adverse Event

Adverse events are classified as serious or non-serious. A **serious adverse event** is any AE that is:

- fatal
- life-threatening
- requires or prolongs hospital stay
- results in persistent or significant disability or incapacity
- a congenital anomaly or congenital disability
- an important medical event

Important medical events are those that may not be immediately life-threatening but are clearly of major clinical significance. They may jeopardize the subject and require intervention to prevent the other serious outcomes noted above. For example, drug overdose or abuse, a seizure that did not result in an in-patient hospitalization, or intensive treatment of bronchospasm in an emergency department would typically be considered serious.

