5.3.2.2. Adverse Events

AEs will be coded using the most recent version of the Medical Dictionary for Regulatory Activities (MedDRA).

A treatment emergent adverse event (TEAE) is defined as an event that has onset date on or after the first day of exposure to infusion treatment and on or before the last day of infusion treatment. Here the first day of exposure is defined as the first day of exposure to infusion treatment.

Treatment Adverse events (TAES) are summarised descriptively, whereas non-TEAEs are presented in listings. TAE data will be displayed in terms of the number of subjects with at least one event (N), percentage of subjects with at least one event (%) and the number of events (E).

Summaries of TAEs and of serious AEs will be presented as an overview including all AEs, serious AEs, AEs by severity, AEs by relation to treatment, action to AEs and treatment advised, and outcome of AEs.

Furthermore, summary tables based on system organ class and preferred terms are made for:

- All TAEs
- Serious AEs

Hope Biosciences Research Foundation HBPCOVID02

• AEs leading to withdrawal of study

Incidence and risk of AEs of special interest (includes serious or nonserious), including thromboembolic events, infections, and hypersensitivities will be summarized based on system organ class and preferred terms.

Individual adverse events will be listed.

The details of the planned displays are in programming specification document.

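### SAP 7.2.2 reverses the treatment-emergent flag, and SAP 5.3.2.2 closes the TEAE window on the last infusion day although the primary safety endpoint runs to Week 26

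*SAP*

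**What the plan says.** The protocol's second primary objective is safety, "as determined by the incidence of adverse events or serious adverse events (Time frame: Baseline to Week 26". Its primary endpoints, assessed as changes from Baseline to Week 26, include "Incidence of treatment-emergent Adverse Events (TEAEs) and serious Adverse Events (SAEs". SAP 2.1 repeats both.

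The SAP then defines treatment-emergent twice.

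- **SAP 7.2.2 (Study Period).** The flag is Y: "If event start date is not missing and is before date of first dose of study medication". The flag is N: "Any event started on or after date of first dose of study medication or event date is missing or partial".
- **SAP 5.3.2.2 (Adverse Events).** A TEAE starts on or after the first day of infusion exposure and "on or before the last day of infusion treatment". Treatment AEs (the label 'TAE' is used without a definition) are summarised, while "non-TEAEs are presented in listings".

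Data collection runs well past the last infusion. Infusions are at Weeks 0, 2, 6 and 10. The instruction for the Week 14 and Week 20 calls is "Assess the incidence of any adverse event since the last visit", and it is repeated for the Week 26 visit. The protocol's Adverse Event Reporting Period extends to about 16 weeks after the last administration. Participants whose infusion is stopped for an adverse event remain in safety follow-up (Infusion Stopping Rules).

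**The concern.** Read literally, 7.2.2 counts as treatment-emergent only what happened before treatment. This looks like a swap of the two rows, but 7.2.2 sits in the appendix of data derivation rules, where a programmer would look for the flag, and it contradicts 5.3.2.2 outright.

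The second problem remains once the labels are put right. Under 5.3.2.2 the window shuts on each participant's own last infusion day. A non-serious event at Week 14, or on the day after the fourth infusion, which the 24-hour contact exists to detect, is a non-TEAE. The summary tables for a named primary endpoint would then describe the infusion period and not the 26 weeks in the objective. The window also varies in length with the number of infusions received: a participant stopped after one infusion has a window of a single day.

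**Working it through.** **Inputs.** Infusions at Weeks 0, 2, 6 and 10 (Protocol, Study Summary); End of Study at Week 26 with ±7-day visit windows (Protocol, Table 1); follow-up of 16 weeks after the last infusion (Protocol, Investigational Plan and Adverse Event Reporting Period); the two flag rules above.

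**The plan's own figure.** 26 − 10 = 16 weeks, which matches the stated follow-up.

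**Flag by onset date, four infusions on schedule.** The last column is the rule proposed under the fix.

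| Onset | 7.2.2 as written | 5.3.2.2 as written | First infusion to Week 26 |
|---|---|---|---|
| 7 days before first infusion | Y | N | N |
| Day of infusion 1 | N | Y | Y |
| Week 6 | N | Y | Y |
| Day of infusion 4 | N | Y | Y |
| Day after infusion 4 | N | N | Y |
| Weeks 14, 20, 26 | N | N | Y |

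The two rules disagree on every dated onset up to the last infusion. After it both give N, so neither rule as written covers Weeks 10 to 26.

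**Follow-up outside the 5.3.2.2 window.**

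- Four infusions: (26 − 10)/26 = 61.5%.
- With visit windows: (25 − 11)/25 = 56.0% to (27 − 9)/27 = 66.7%.
- Last infusion at Week 6: (26 − 6)/26 = 76.9%. At Week 2: (26 − 2)/26 = 92.3%. Both take the objective's 26 weeks as the denominator.

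**Share of events dropped.** The documents give no adverse event rates, so this part rests on assumptions. Let the Weeks 0–10 rate be r times the later rate. The share starting after Week 10 is 16/(10r + 16):

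- r = 1: 16/26 = 61.5%
- r = 2: 16/36 = 44.4%
- r = 3: 16/46 = 34.8%
- r = 5: 16/66 = 24.2%

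**Participants with at least one TEAE.** If events are Poisson and the true 26-week incidence is p, the incidence reported under 5.3.2.2 is 1 − (1 − p)^(10r/(10r + 16)):

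| Assumed true p | r = 1 | r = 2 | r = 5 |
|---|---|---|---|
| 50% | 23.4% | 32.0% | 40.9% |
| 80% | 46.2% | 59.1% | 70.5% |

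**The case against.** The best defence is that the SAP nearly has the right rule already. With its labels swapped back, 7.2.2 treats anything starting on or after the first dose as treatment-emergent, with no end date, and that would cover all events collected to Week 26. This is true, but the SAP would then hold an open-ended window in one section and a closed one in the other, with nothing to say which governs. All the figures above are conditional on 5.3.2.2 governing.

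Other points on that side:

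- **Later events are not lost.** They are listed, and the serious, special-interest and withdrawal tables are not expressly limited to TEAEs. This stands. The overview in 5.3.2.2 also refers to all AEs, but within a sentence about summaries of TAEs and serious AEs, so it does not settle whether later non-serious events are counted. Those are the events clearly at risk.
- **An on-treatment window is a legitimate choice.** It is, as a labelled supplement. Here it is the SAP's only explicit window with an end date, it does not match the endpoint's time frame, and SAP 5.4 declares no departure from the protocol.
- **The Study Summary gives a treatment duration of 26 weeks.** Section 5.3.2.2 refers to infusion treatment, and the Investigational Plan and Treatment Regimen give 10 weeks. At most this adds ambiguity.
- **The early-stopper shares depend on the denominator.** If follow-up ends 16 weeks after the last infusion, they become 16/22 = 72.7% (Week 6) and 16/18 = 88.9% (Week 2). The conclusion is unchanged.
- **The event-loss figures are illustrative.** Agreed. Only the share of follow-up time comes from the documents.

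**Conclusion.** The concern holds on both counts. The flag in 7.2.2 is reversed against 5.3.2.2, and as written neither section yields TEAE incidence over Baseline to Week 26, a named primary safety endpoint. Under 5.3.2.2 the summary omits 16 of 26 weeks (61.5%) for a participant given all four infusions, and a larger share for one who stops early.

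How many events that omits depends on when they occur. Over the assumed early-to-late rate ratios of 1 to 5, between 61.5% and 24.2% of events would be left out. Whether the comparison between arms is biased depends on event timing and on differential stopping, which the documents do not give, so no direction of bias is claimed. This must be corrected before the analysis: it changes a primary safety result, and a change made after unblinding would be open to challenge.

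**What to change.** 1. Swap Y and N in SAP 7.2.2.
2. Put one TEAE definition in both 7.2.2 and 5.3.2.2: onset or worsening on or after the start of the first infusion, through the Week 26/End of Study visit. Including worsening follows the protocol's own definition of an adverse event: "any symptom, sign, illness, or experience that develops or worsens in severity during the study".
3. Apply the flag after the partial-date imputation in 7.2.6. Count an event whose start date is still missing as treatment-emergent unless the known date parts or the stop date place onset before the first infusion.
4. Replace the undefined 'TAE' with 'TEAE', and state for the serious, special-interest and withdrawal tables whether they include all AEs or only TEAEs.
5. If an infusion-period summary is also wanted, add it as a separate, labelled on-treatment table.

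The cost is SAP wording and one derivation. TEAE counts will be higher than under 5.3.2.2. No further data are needed, because adverse events are already collected to Week 26.

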7.2.3. Study Day and Reference Dates

Study Day

- Study Day 1 is defined as the day the first dose was taken.
- Study day >1 is calculated as the number of days from the date of the Study Day 1:
 - Ref Date = Missing \rightarrow Study Day = Missing
 - Ref Date < Date of Study Day 1 \rightarrow Study Day = Ref Date Date of Study Day 1
 - Ref Data \geq Date of Study Day 1 \rightarrow Study Day = Ref Date (Date of Study Day 1)
 - + 1

7.2.4. Assessment Window

For data summaries by visit, scheduled visits with nominal visit description will be displayed. Unscheduled visits will not be displayed or slotted into a visit window. While in the baseline derivation or post-baseline worst scenarios are derived, unscheduled visits are considered. All unscheduled visits will be displayed in listings, as appropriate.

7.2.5. Multiple measurements at One Analysis Time Point

For lab tests on a study day, if more than one assessment is taken on the same day, the test from the latest non-missing lab measurements will be used for the analysis. All lab measurements will be displayed in the listings, as appropriate.

Element	Reporting Detail		
General	• Partial dates will be displayed as captured in participant listing displays.		
Adverse Events	 Partial dates will be displayed displays. Partial dates for AE recorded i following conventions: Missing start day 	 in the CRF will be imputed using the If study intervention start date is missing (i.e, subject did not start the study medication), then set start date = 1st of month. Else if study intervention start date is not missing: If month and year of start date = month and year of study intervention start date, then If stop date contains a 	
		 full date and stop date is earlier than study intervention start date, then set start = 1st of month. o Else set start date = study intervention start date. Else set start date = 1st of month 	

7.2.6. Handling of Missing and Partial Dates

Element	Reporting Detail		
	Missing start day and month	 If study intervention start date is missing (ie., subject did not start study medication), then set start date = January 1. Else if study intervention start date is not missing: If year of start date = year of study intervention start date, then If stop date contains a full date and stop date is earlier than study intervention start date = January 1. Else set start date = January 1. 	
	Missing end day	A '28/29/30/31' will be used for the day (dependent on the month and year)	
	Missing end day and month	No imputation	
	Completely missing start/end date	No imputation	

Element	Reporting Detail	
Concomitant Medications	Partial dates for any concomitat will be imputed using the follow	nt medications recorded in the CRF wing convention:
	Missing start day	If study intervention start date is missing (i.e, subject did not start the study medication), then set start date = 1 st of month.
		 date is not missing: If month and year of start date = month and year of study intervention start date, then If stop date contains a full date and stop date is earlier than study intervention start date,
		 then set start = 1st of month. Else set start date = study intervention start date. Else set start date = 1st of month
	Missing start day and month	If study intervention start date is missing (ie., subject did not start study medication), then set start date = January 1.
		 Else if study intervention start date is not missing: If year of start date = year of study intervention start date, then If stop date contains a full date and stop date is earlier than study intervention start date, then set start date = January
		 Else set start date = study intervention start date. Else set start date = January 1.

Element	Reporting Detail		
	Missing end day	A '28/29/30/31' will be used for the day (dependent on the month and year)	
	Missing end day and month	A '31' will be used for the day and 'Dec' will be ised for the month	
	Completely missing start/end date	No imputation	

8. **REFERENCES**

^[1]Cohen J. Statistical power analysis for the behavioral sciences. 2nd ed ed. Hillsdale, N.J.: L. Erlbaum Associates Hillsdale, N.J.; 1988.

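### SAP 7.2.2, 7.2.6 and 5.3.2.2 disagree on whether an adverse event with a partial or missing onset date is treatment emergent, and correcting the reversed Y/N labels does not cure it

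*SAP*

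**What the plan says.** Three parts of the SAP bear on the status of an adverse event (AE) with an incomplete onset date.

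- **SAP 5.3.2.2 (Adverse Events)** defines a treatment-emergent AE (TEAE) by date. To qualify, the AE "has onset date on or after the first day of exposure to infusion treatment and on or before the last day of infusion treatment". TEAEs are summarised, "whereas non-TEAEs are presented in listings".
- **SAP 7.2.6 (Handling of Missing and Partial Dates)** imputes partial AE onsets. If only the day is missing and the month is that of the first infusion, the first-infusion date is used unless a full stop date is earlier. In any other month the first of the month is used: "Else set start date = study intervention start date. Else set start date = 1st of month". This row of the table is printed just above the 7.2.6 heading. For the entry "Completely missing start/end date" the rule is no imputation.
- **SAP 7.2.2 (Study Period)** assigns status directly. Y goes to events with a known start before the first dose. N goes to "Any event started on or after date of first dose of study medication or event date is missing or partial". These labels are the reverse of 5.3.2.2, which is a defect in its own right.

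The 7.2.6 cell for an AE onset with day and month missing reads, in part, "stop date is earlier than study intervention start date = January 1. Else set start date = January 1". The matching concomitant-medication row reads "Else set start date = study intervention start date. Else set start date = January 1".

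**The concern.** SAP 7.2.2 gives every partial onset one status, whatever month or year was recorded. SAP 7.2.6 turns the same partial onsets into dates, some before the first infusion and some after, and 5.3.2.2 then classifies by date. The SAP does not say which step comes first. Two programmers who each follow it faithfully could classify the same event differently.

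A completely missing onset raises a further problem. With no date it cannot satisfy the 5.3.2.2 condition, so the event leaves the TEAE tables even when its stop date shows that it was present after dosing began.

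TEAE incidence is among the primary endpoints (Protocol, Primary Endpoints; SAP 2.1), so its counting rule should give one answer per event.

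**Working it through.** The plan has no figure to reproduce; this is a check of classification rules.

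**Inputs**

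- First infusion: 20 July 2022. This is an assumption, later than the May 2022 IRB approval; the documents give no infusion dates.
- Last infusion: Week 10 by the schedule, 20 July + 70 days = 28 September 2022. The TEAE window under 5.3.2.2 is then 20 July to 28 September 2022.
- Imputation: the SAP 7.2.6 AE rows for a missing day and for a completely missing date. Neither depends on the January 1 cell.

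**Four records under each rule**

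| Recorded onset | Date under 7.2.6 | 5.3.2.2 | 7.2.2 as printed | 7.2.2 with labels swapped |
|---|---|---|---|---|
| *Jun 2022* | 1 Jun 2022 | not TEAE | N (agrees) | Y (conflicts) |
| *Jul 2022*, no earlier full stop date | 20 Jul 2022 | TEAE | N (conflicts) | Y (agrees) |
| *Aug 2022* | 1 Aug 2022 | TEAE | N (conflicts) | Y (agrees) |
| missing, stopped 15 Sep 2022 | none | not TEAE | N (agrees) | Y (conflicts) |

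Each labelling conflicts with 5.3.2.2 on two of the four records. The cause is structural. The three partial dates share one row of 7.2.2, but imputation puts one before the first infusion and two on or after it. No single label can fit all three.

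**Completely missing onset.** No imputation means no date, and 5.3.2.2 needs a date. The event is therefore not a TEAE, whatever its stop date. As printed, 7.2.2 reaches the same answer. Once its labels are corrected, it reaches the opposite one.

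**Size per participant.** 80 participants randomised 1:1 gives 80 / 2 = 40 per arm. If the misclassified event is a participant's only one, that arm's TEAE incidence moves by 1 / 40 = 2.5 percentage points. If the participant has another TEAE, the incidence does not move.

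**January 1 cell, conditional on its wording.** Read literally, both visible outcomes are January 1. A year-only onset in the infusion year would then fall before the first infusion on 364 of 365 possible first-infusion days, the exception being January 1 itself. If the cell has the branch found in the medication row, and no full stop date precedes the first infusion, the onset is set to the first-infusion date and is a TEAE on 365 of 365.

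**The case against.** **Impute, then classify.** The strongest reply is that imputing first is the natural order, since 7.2.6 says that partial AE dates are imputed. On that reading *Jun 2022* becomes 1 June and is before dosing, and corrected 7.2.2 labels would give the right answer. It can be added that *Jun 2022* is not a missing date and could be read into the before-first-dose row. The order is sensible, but the SAP does not state it. It would also leave the mention of partial dates in 7.2.2 with almost no function, because 7.2.6 gives a date to month-year and year-only onsets. The N row names partial dates expressly.

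**Missing onset.** It can be argued that, once the labels are swapped, 7.2.2 already supplies a rule for missing onsets, with 5.3.2.2 as the general definition. That is close to the remedy proposed here, but the SAP does not say that 7.2.2 overrides 5.3.2.2.

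**Few events, no arm difference.** This stands. AEs are assessed at every visit from Visit 2, with a contact 24 hours after each infusion, so badly incomplete onsets should be uncommon. The date rules are the same in both arms. The SAP's tables of serious AEs and of AEs leading to withdrawal, and its summaries of AEs of special interest, are not worded as limited to TEAEs, so a misclassified event need not vanish from them.

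**Stronger readings that the documents do not support.** A reader might infer that the SAP sets every year-only AE onset to January 1 and so removes it from the TEAE tables. That sentence has no clause stating what to set, and its stop-date test changes nothing. Two neighbouring rows contain the branch to the first-infusion date. The cell looks like table text lost in reading the PDF, so it is a query and not a finding. A reader might also infer that 7.2.2 as printed brings partially dated pre-dose events into the TEAE tables. It labels them N; that error would appear only after the labels are swapped.

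**Conclusion.** The inconsistency is real and rests on intact text. SAP 7.2.2 cannot agree with 5.3.2.2 plus 7.2.6 under either labelling, and a completely missing onset cannot be a TEAE under 5.3.2.2. Repairing the Y/N labels alone leaves both problems in place.

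The practical size is probably small. The documents give no frequency of incomplete onset dates, so the number of affected events cannot be estimated. The effect on incidence is at most 2.5 points per affected participant, assuming 40 per arm, and no difference between arms is shown. The July 2022 infusion date is only illustrative: for other infusion dates the same conflict arises between a month wholly before the first infusion and a later month within the window.

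It should be corrected because it concerns a primary safety endpoint and the repair is minor. The January 1 cell is no part of this conclusion.

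**What to change.** When the reversed labels in SAP 7.2.2 are corrected, state one rule in both 5.3.2.2 and 7.2.2:

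1. Apply the 7.2.6 imputation first, then classify by the resulting date.
2. Delete the words *or partial* from the 7.2.2 row.
3. Treat a completely missing onset as treatment emergent unless a full stop date precedes the first infusion.

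Separately, check the AE cell for missing day and month in 7.2.6 against the source document. If it really gives January 1 in both branches, align it with the AE missing-day row and the concomitant-medication row, which set the first-infusion date where no earlier full stop date exists.

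The cost is a few lines of SAP text and derivation code before database lock. The downside is that a few events that truly began before dosing may be counted as TEAEs, which would slightly raise reported incidence under a rule common to both arms.
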